In contrast to the previous studies, Strijbos et al¹⁵ were successful in maintaining (and indeed improving) pulmonary rehab gains following 12 weeks of home-care rehabilitation. The investigators speculate that patients had become accustomed to exercise in their own domiciliary environment. This made it easier for them to continue exercising at home after the initial 12-weeks of training were over. A similar result was recently reported in the small proof-of-principle study of Ho et al.⁵⁸

The observations of Strijbos et al¹⁵ and Ho et al.⁵⁸ combined with our success in increasing exercise performance with RAS-enhanced music (see *preliminary results*, **Section B.6.1.**) lay the scientific foundation of the proposed experiments in our *Objective #3*. Specifically, these observations raise the possibility that combining RAS-music and home-based exercise training will result in greater long-term maintenance of rehabilitation gains than exercise-training alone.

A.3.4. Potential Confounders. Potential confounders to any pulmonary rehabilitation study include the patients' physiological and psychological phenotype and clinical factors.

A.3.4.1. Potential Confounders: Physiological Phenotype. Decreased exercise tolerance with attendant difficulty in achieving sufficient intensity of exercise during training hinders the effectiveness of rehab.⁶³ In addition to severity of lung disease, independent predictors of decrease exercise tolerance include quadriceps dimension, recruitment and strength, systemic inflammation (hsCRP and IL-6)⁶⁴ (see *work accomplished*).

A.3.4.2. Potential Confounders: Psychological Phenotype. Depression,^{49,60,65} anxiety^{49,60,65} and overall sense of fatigue^{62,66} can limit the effectiveness of pulmonary rehab as these factors may cause insufficient adherence to rehabilitation programs.

A.3.4.3 Potential Confounders: Clinical Factors. Approximately 15% of patients drop out from pulmonary rehab due to clinical factors such as COPD exacerbations,⁶⁷ cardiovascular disease (myocardial infarction, cerebrovascular accidents), or cancer.⁶⁸ Because of this, in the proposed investigation, we will assess the influence of the physiological and psychological phenotype and clinical factors on the effectiveness of RAS- enhanced and non RAS-enhanced home-based

rehabilitation (*Objective #4*).

A.4. Significance and Relevance to the VA.

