C.1.9.5. Questionnaires: Self-reported physical function and quality of life will be evaluated using eight questionnaires (see **C.1.9.5.a. to C.1.9.5.e.**).

C.1.9.5.a. Chronic Respiratory Disease Questionnaire (CRQ). This questionnaire is designed to determine how the lives of patients with chronic airflow limitation are affected by the illness and the perceived impact of symptoms and limitations on quality of life.¹¹² Test-retest reliability and validity of the CRQ are well established.¹¹² Patients will not be informed of their previous responses on the questionnaire when the CRQ is administered at week 6 and 12 and 24. CRQ scores will be used as covariates in the final analysis if appropriate (see **C.2 Statistical Analysis**).

C.1.9.5.b. Short Form-36 Health Survey (SF-36): This is a general health-related quality of life

instrument to quantify perceived physical function and mental health.⁸ The SF-36 will be used to describe the sample and to have a comparator measure to published clinical pulmonary rehabilitation programs.¹¹³

C.1.9.5.c. Charlson Comorbidity Index. This validated¹¹⁴ and widely utilized index^{80,82} will be used to determine whether comorbidities influence study outcomes (see **C.2 Statistical Analysis**).

C.1.9.5.d. Depression and Anxiety. To control for the influence of ongoing depression and anxiety on adherence, the Center for Epidemiologic Studies Depression Scale (CES-D)¹¹⁵ and the State-Trait Anxiety Inventory (STAI)¹¹⁶ will be administered at baseline and at major data collection time-periods. CES-D and STAI scores will be used as covariates in the final analysis as appropriate.

C.1.9.5.e. Self-Efficacy. The Self-Efficacy for Walking¹¹⁷ and the Self-Efficacy for Shortness of Breath questionnaires¹¹⁸ will be used to measure self-efficacy at all time periods.¹¹⁷ These are reliable and valid¹¹⁸ instruments designed to assess a patient's confidence in keeping shortness of breath from interfering from walking or from doing what they want to do.

C.1.9.5.f. COPD Assessment Test The COPD Assessment Test (CAT) measures the impact COPD has on patient's well-being and daily life.

C.1.9.5.g Coronavirus Anxiety Scale (CAS) Assesses dysfunctional anxiety associated with the COVID19

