In the statistical analysis of H_3 , we will use independent t-tests to compare the changes in measured function (distance walked in the 6MWT and perceived function (questionnaires) between 12 and 24-weeks between the RAS-music and the no-music groups. We will also conduct paired t-tests within each group to determine whether values at 24 weeks are worse than those at 12 weeks. These computations will be based on those patients with 12 and 24-week data. To assess whether patients included in the H_3 analysis are representative of the original randomized groups, we will also compare demographic and health measures (i.e., FEV₁ percent predicted, comorbidities, depressive symptoms and exacerbations) of patients included in the H_3 analysis to patients who were not.

C.2.3. Statistical Analysis: Exploratory objective: [exploratory objective not reported]

TO ASSESS IMPACT OF PHYSIOLOGICAL AND PSYCHOLOGICAL PHENOTYPE AND CLINICAL FACTORS ON RESPONSIVENESS TO REHABILITATION ACHIEVED WITH AND WITHOUT CONCURRENT USE OF RAS-MUSIC. PHYSIOLOGICAL FACTORS INCLUDE: SYSTEMIC INFLAMMATION (HS-CRP), QUADRICEPS STRENGTH, RECRUITMENT AND FATIGUE, QUADRICEPS FUNCTION AND DIMENSION AFTER REHABILITATION. PSYCHOLOGICAL FACTORS INCLUDE: SELF-EFFICACY, ANXIETY AND DEPRESSION. CLINICAL FACTORS INCLUDE: ADHERENCE TO THE 12-WEEK PROGRAM, ADHERENCE TO FOLLOW-UP AND NUMBER AND SEVERITY OF EXACERBATIONS.

To assess the impact of the above confounders two separate analyses will be conducted: (a) A linear regression model with changes from baseline to 12 weeks of training as the dependent variable, and assigned treatment group, physiologic and psychologic phenotype and clinical factors as the independent variables, and

(b) A mixed model ANOVA with baseline, and 12 and 24 weeks measurements as dependent measures and assigned group, physiologic and psychologic phenotype and clinical factors as the independent variables.

C.3. Expected Outcome: We expect to demonstrate that improvements in 6-minute walking distance from baseline to 12 weeks will be greater after completing 12 weeks of a home-based, exercise program with RAS- music than after a home-based, exercise program without music.

C.4. Alternative Outcomes. Our primary hypothesis will be rejected if, at 12 weeks, improvements in 6-minute walking distance are not greater with exercise-training plus RAS-music than with exercise-training without music. In this case, at least three alternative outcomes will be considered.

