Two, RAS-music adds nothing to gains achieved with exercise-training alone. Two mechanisms could cause this unlikely^{11,58} result: (1) insufficient stress on muscles and (2) suboptimal entrainment. The first possibility would be supported if prevalence of exercise-induced quadriceps fatigue elicited by a typical exercise-training session in the two groups is the same. The second possibility would be supported if less gains are related to greater failure to entrain gait during teaching sessions (*poor entrainers*). If that happens, we plan future studies where RAS-music in *poor entrainers* will be optimized – i.e., in the subgroup of *poor entrainers* we will increase the volume of RAS music and augment the entraining pulse (strongly emphasized beat) to facilitate music-motor synchronization.²⁷

Three, the positive impact of RAS-music is smaller than predicted – i.e., Type II error.

C.4.3. Alternative Outcome #3. Neither group experiences improvement in 6-minute walking distance. If this occurs at least three possibilities must be considered.

One, neither group engaged in home-based exercise training. Several factors, including psychological phenotype (i.e., anxiety, depression)¹²² are known to reduce acceptance and adherence to rehab.^{7,8,12,57,58} If our data demonstrate that psychological factors interfere with acceptance and adherence to home rehab (see *Explorative Objective*), we will plan a future investigation that will include formal psychological interventions (i.e., cognitive behavioral therapy) to address those factors.¹²³

Two, physiological/clinical factors decreased exercise tolerance thereby curbing intensity of exercise during training.⁶³ These factors could include frequency of exacerbations, severity of lung disease, quadriceps dimension, recruitment and strength, systemic inflammation (hsCRP) (see *Explorative Objective*).⁶⁴ If the negative results of our study parallel these physiological/clinical factors, we will explore the possibility of combining pulmonary rehab with the administration of novel anti-inflammatory agent(s). This strategy is based on the mounting evidence that systemic inflammation may contribute to local and systemic manifestations of COPD.¹²⁴ Additional ancillary interventions could include strategies to enhance muscle anabolism,^{125,126} to enhance muscle recruitment by the central nervous system,¹²⁷ and strategies to promote muscle overload (fatigue) during training.^{41,128}

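### C.4.3 relies on the Exploratory Objective to show whether anxiety and depression interfere with adherence, but neither C.2.3 model has adherence as its outcome and both adjust for it

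*Combined protocol and SAP*

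**What the plan says.** Section C.4.3 deals with the case where neither group improves. Its first explanation is that patients did not engage with home training. It says that several factors, anxiety and depression among them, "are known to reduce acceptance and adherence to rehab". It then sets a conditional step: "If our data demonstrate that psychological factors interfere with acceptance and adherence to home rehab", with a cross-reference to the Exploratory Objective, a future study with formal psychological treatment will be planned. Section C.4.2 sends the case of poor compliance with the music to the same place.

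Section C.2.3 is where the Exploratory Objective is analysed. Model (a) is "A linear regression model with changes from baseline to 12 weeks of training as the dependent variable", with "assigned treatment group, physiologic and psychologic phenotype and clinical factors as the independent variables". Model (b) is a mixed model whose outcomes are the baseline, week-12 and week-24 values, with the same kinds of predictor. The psychological factors are self-efficacy, anxiety and depression. The plan spells out the clinical factors: "CLINICAL FACTORS INCLUDE: ADHERENCE TO THE 12-WEEK PROGRAM, ADHERENCE TO FOLLOW-UP AND NUMBER AND SEVERITY OF EXACERBATIONS".

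Two other sections bear on the link. Section A.3.4.2 says that depression, anxiety and fatigue "can limit the effectiveness of pulmonary rehab as these factors may cause insufficient adherence to rehabilitation programs". Section C.1.9.5.d gives the reason for collecting the depression scale (CES-D) and the anxiety scale (STAI): "To control for the influence of ongoing depression and anxiety on adherence". It plans to use the scores as covariates.

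**The concern.** C.4.3 asks whether psychological state affects adherence. An analysis that answers this needs adherence on the left-hand side. In C.2.3 adherence appears only on the right-hand side.

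A second problem affects the nearest substitute, the psychological coefficients in the response models. On the path given in A.3.4.2, low mood leads to poor adherence, which leads to less benefit. Adherence is then a mediator. A coefficient for depression with adherence held fixed describes only the effect that does not pass through adherence.

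At stake is the reading of a null trial. Someone who follows the C.4.3 cross-reference would look at the psychological coefficients in C.2.3. They could find little there when these factors act by the very route the plan proposes, and could set that explanation aside for the wrong reason.

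**Working it through.** **Structure.** The documents give no figure for this point, so the main check is to compare what C.4.3 needs with what is specified.

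| Place | Outcome | Role of adherence |
|---|---|---|
| C.4.3 (needed) | adherence | outcome |
| C.2.3 model (a) | change from baseline to week 12 | predictor |
| C.2.3 model (b) | baseline, week-12 and week-24 values | predictor |
| C.1.9.5.d | not named (CES-D and STAI as covariates) | not modelled |
| C.2.2, H3 representativeness check | none (compares patients in and out of the H3 analysis) | not modelled |
| C.4.2 | barriers to compliance to be investigated, no method given | not modelled |

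No section specifies a model with adherence as the outcome. C.2.3 does not name its response variable, but it cannot be adherence, because adherence is listed among the predictors.

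**Illustration of the adjustment.** From C.1.3: 170 randomised and about 8% attrition at week 12, so 170 × 0.92 = 156.4, about 156 patients. The figure of 136 in C.1.3 allows for losses to week 24. Everything else is assumed and is not in the documents:

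- correlation of depression with adherence, r = −0.3 (range −0.2 to −0.4)
- standardised effect of adherence on gain, b = 0.5
- direct effect of depression on gain, d = 0
- reliability of measured adherence, ρ = 1
- residual variance of gain, 1 − b² = 0.75
- two-sided 5% test

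With d = 0, the depression coefficient is:

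- without adherence in the model: rb = −0.3 × 0.5 = −0.15
- with adherence in the model: rb(1 − ρ)/(1 − ρr²), which is 0 when ρ = 1
- with adherence as outcome: r√ρ = −0.3 when ρ = 1

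Detection is approximately Φ(λ − 1.96), where λ = |coefficient| × √(n × V)/σ. V is the predictor's variance after the other predictors, and σ is the residual SD.

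- Without adherence: λ = 0.15 × 12.490/√0.9775 = 1.895, giving 47% (simulation 46%).
- With adherence: the coefficient is 0, so detection is the nominal 5%.
- Adherence as outcome: λ = 0.3 × 12.490/√0.91 = 3.928, giving 97.5% (simulation 97%).

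Simulated detection of depression, n = 156, b = 0.5, d = 0, ρ = 1:

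| r | with adherence (C.2.3) | without adherence | adherence as outcome |
|---|---|---|---|
| −0.2 | 5% | 24% | 71% |
| −0.3 | 5% | 46% | 97% |
| −0.4 | 5% | 70% | over 99% |

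**Relaxing the two strong assumptions** (r = −0.3):

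- Adherence measured with reliability 0.6: the adjusted coefficient is −0.15 × 0.4/(1 − 0.6 × 0.09) = −0.060/0.946 = −0.063. The C.2.3 form detects it in about 13% of runs. With adherence as outcome, λ = 0.3 × √0.6 × 12.490/√0.946 = 2.98, about 85%.
- Direct effect of −0.15 SD, error-free adherence: the adjusted coefficient is −0.15 and λ = 0.15 × √(156 × 0.91)/√0.75 = 2.06, about 53% to 54%. Even so, it describes only the direct half of a total effect of −0.15 + (−0.15) = −0.30.

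**The case against.** The strongest reply is that little depends on this. C.2.3 is exploratory, and its heading carries a bracketed note that the objective is not reported. The C.4.3 sentence applies only to a null result and leads only to planning another study. This is right, and it limits the weight of the point. It does not make the cross-reference correct.

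The percentages can also be challenged. A.3.4.2 says only that psychological factors may act through adherence, not that this is the sole route. Section C.1.9.4 reports that wrist-worn Fitbits can undercount steps by 11% to 16%. So the effect may be weakened rather than lost, as the relaxed cases show. And if almost nobody exercised, adherence would have little spread. With adherence dichotomised at about 10% adherent and the other assumptions unchanged, the model with adherence as outcome detects depression in about 61% of runs, not 97%. All of this stands, so the figures show direction only.

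The H3 check compares depressive symptoms in patients with and without week-12 and week-24 data. That concerns retention rather than exercise, and it omits anxiety.

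Three stronger readings are tempting but unsupported:

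- **That adjustment removes the effect C.4.3 seeks.** The effect of psychology on adherence is absent from the models. What adjustment takes out is its trace in the response.
- **That patients lost by week 12 are mainly the least adherent.** The documents do not say so. A patient who never walks can still attend week 12, and A.3.4.3 attributes dropout to exacerbations, cardiovascular disease or cancer.
- **That the question cannot be answered.** CES-D, STAI, self-efficacy and Fitbit data are all collected. The analysis is unspecified, not impossible.

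**Conclusion.** The point holds in two parts. First, from the text alone, the effect on which C.4.3 bases its next step is not estimated by either C.2.3 model or anywhere else in the plan. Second, given the plan's own path in A.3.4.2, entering adherence beside the psychological factors strips out the part of their effect on response that runs through adherence. The loss is complete only if adherence is well measured and there is no direct effect; otherwise it is partial.

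The size depends on path strengths that the documents do not give. Under the assumptions shown, the C.2.3 form detects depression in about 5% of trials with error-free adherence, about 13% at reliability 0.6, and just over half with a direct effect of −0.15 SD. The consequence is confined to an exploratory analysis and the planning of a future study. The primary 6-minute walk comparison and the secondary hypotheses do not depend on it. The change is worth making because it is cheap and the plan has said that it will act on the answer.

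**What to change.** 1. In C.2.3, add a model with adherence to the 12-week programme as its outcome, in all randomised patients, on baseline CES-D, STAI, self-efficacy and assigned group.
2. Define the adherence measure beforehand, for example from the Fitbit data already collected. Table 4 names step counts for adherence, but the plan gives no metric or threshold.
3. State how withdrawals are scored, with a sensitivity analysis for withdrawals for medical reasons, so that an exacerbation or a cancer diagnosis is not simply counted as behavioural non-adherence.
4. Point the C.4.3 sentence to this model. That sentence also mentions acceptance, so define it or limit the sentence to adherence.
5. For the psychological factors, fit models (a) and (b) without adherence. Label any adherence-adjusted version as the part of the effect that does not act through adherence.

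The cost is SAP wording, an adherence definition and one or two more exploratory regressions on data already collected. No visits or patients are added. The definition will take some thought, and the added model may have limited power if adherence is uniformly low.

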C.4.1. Alternative Outcome #1: Improvements in 6-minute walking distance are greater after exercise-training without music. If this occurs, at least three possibilities must be considered.

One, despite efforts to optimize randomization (see **C.1.5.**), the RAS-music group experienced less severe quadriceps fatigue or other confounders than the exercise-alone group (e.g., imbalance in the randomization at baseline of fitness or history/likelihood of exacerbations) (see *Explorative Objective*). If this occurs, we will conduct a future study focused on patients with more severe COPD who have smaller

quadriceps and develop less fatigue during exercise and who are stratified according to baseline fitness and history/likelihood of exacerbations.

Two, patients paid more attention to the RAS-music than to the assigned exercise (inadequate exercise intensity during training). Less exercise intensity would reduce potential gains obtainable with rehab. Although we consider this possibility very unlikely,^{11,58} we will objectively test for sub-optimal challenge of the leg muscles (lack of contractile fatigue; see *section A.3.2.1.*) by recording Quad-Twitches at the end of training.⁴⁴

C.4.2. Alternative Outcome #2. If improvements in 6-minute walking distance are similar in the two groups at least three possibilities must be considered.

One, the RAS-music group did not comply with RAS during training. To monitor and optimize adherence with RAS-music plus exercise we developed a very rigorous protocol (see *section C.1.7.*). If, despite our adherence protocol, compliance remains poor we will investigate possible barriers to poor compliance and plan future studies to address barriers (see **C.4.3. Alternative Outcome #3**).

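### C.4.3 and C.4.1 look to the exploratory objective to judge lung-disease severity and baseline fitness, but the factors listed for the C.2.3 models include neither, and model (a) omits baseline 6MWT (minor)

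*Combined protocol and SAP*

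**What the plan says.** C.4 sets out how the team will explain a disappointing result. Under C.4.3 (neither group improves), one explanation is that physiological or clinical factors limited training: "These factors could include frequency of exacerbations, severity of lung disease, quadriceps dimension, recruitment and strength, systemic inflammation (hsCRP"). That sentence ends with a pointer to the exploratory objective. Under C.4.1 (the no-music group does better), the example given is "imbalance in the randomization at baseline of fitness or history/likelihood of exacerbations", with the same pointer.

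C.2.3 is the analysis for that objective. Its first list reads: "PHYSIOLOGICAL FACTORS INCLUDE: SYSTEMIC INFLAMMATION (HS-CRP), QUADRICEPS STRENGTH, RECRUITMENT AND FATIGUE, QUADRICEPS FUNCTION AND DIMENSION AFTER REHABILITATION". The other two lists hold three psychological measures (depression, anxiety, self-efficacy), two kinds of adherence, and how many exacerbations occurred and how severe they were. Objective 4 in A1 has essentially the same list. C.2.3 then ties two models to the confounders listed just above them. Model (a) is a linear regression of change from baseline to 12 weeks on group and the listed kinds of factor. Model (b) is a mixed-model ANOVA with baseline, 12-week and 24-week measurements as outcomes and the same predictors.

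Two other sections bear on this. A.3.4.1 states: "In addition to severity of lung disease, independent predictors of decrease exercise tolerance include quadriceps dimension, recruitment and strength". C.1.9.5.c says the Charlson index "will be used to determine whether comorbidities influence study outcomes" and refers the reader to C.2 as a whole.

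**The concern.** The team is to judge from the exploratory objective whether severity of lung disease or baseline fitness explains the response, yet the models as listed contain no term for either. Those explanations cannot be checked where C.4 says they will be.

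The factors that are listed also become harder to interpret. A.3.4.1 sets the quadriceps measures beside lung-disease severity as predictors of exercise tolerance. If a quadriceps, inflammation or mood measure tracks FEV1 or baseline walking distance, and those are left out, its coefficient may carry part of their association with the gain. C.4.3 would use such findings to choose follow-on work: anti-inflammatory, muscle-anabolic, muscle-recruitment or psychological interventions.

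**Working it through.** **1. Compare the lists.**

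| Factor | Named by | In the C.2.3 lists? |
|---|---|---|
| Severity of lung disease | C.4.3 | No |
| Baseline fitness | C.4.1 | No; baseline is part of the outcome in (a) and a repeated outcome in (b) |
| Frequency of exacerbations | C.4.3 | Yes (number and severity) |
| History or likelihood of exacerbations | C.4.1 | Not by name |
| Quadriceps measures, hsCRP | C.4.3 | Yes |
| Comorbidity (Charlson) | C.1.9.5.c, pointing to C.2 generally | No |

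Elsewhere in C.2, FEV1 and comorbidities are named only in the H3 comparison of patients included and not included (C.2.2).

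**2. Reproduce the plan's sample size.** Inputs from C.1.3: SD 232 ft, correlation 0.70, gain 87.2 ft against no change, two-sided 0.05.
- SD of change = 232 × √(2 × (1 − 0.70)) = 179.7 ft.
- 80% power needs 67 per group; 68 per group gives 80.8%. The stated 68 and 80% reproduce.
- 68 × 2 = 136; 136/0.80 = 170; 170/0.70 = 243. These also reproduce. I use n = 136 below.

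**3. Baseline 6MWT left out of model (a).** With equal SDs, the correlation of change with baseline is −(1 − ρ)/√(2(1 − ρ)) = −√((1 − ρ)/2). At ρ = 0.70 this is −√0.15 = −0.387. It follows from the plan's own inputs and needs no assumption that fitness alters training response.

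Take a listed factor with no association with change once baseline is held fixed, and let it correlate r with baseline. Its apparent standardized coefficient is c = −0.387 × r. With SE = √((1 − c²)/(n − 3)) and t = |c|/SE, the chance of declaring it significant is Φ(t − 1.96) + Φ(−t − 1.96).
- r = 0.1: c = −0.039, chance 7.3%.
- r = 0.2: c = −0.077, chance 14.6%.
- r = 0.3: c = −0.116, SE = √(0.9866/133) = 0.086, t = 1.35, chance 27.1%.

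C.1.3 also reports pilot correlations of 0.76 to 0.86. At ρ = 0.86 the change-baseline correlation is −0.265, and the chance is 6.1% at r = 0.1 and 15.1% at r = 0.3. The values of r are assumed; the documents give none.

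**4. FEV1 left out of either model.** Let b be the standardized effect of FEV1 on the gain and r its correlation with the listed factor. The apparent coefficient is b × r, and the formula for the chance is the same. Both b and r are assumed.

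| b | r = 0 | r = 0.1 | r = 0.2 | r = 0.3 | r = 0.5 |
|---|---|---|---|---|---|
| 0.2 | 5.0% | 5.6% | 7.5% | 10.7% | 21.2% |
| 0.3 | 5.0% | 6.4% | 10.7% | 18.1% | 41.7% |
| 0.4 | 5.0% | 7.5% | 15.2% | 28.6% | 65.3% |

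A simulation (3,000 runs per setting, n = 136, group term included) gave 10.0% at b = 0.2, r = 0.3 and 64.5% at b = 0.4, r = 0.5. Both fell to 4.8% once the omitted factor was added.

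Steps 3 and 4 test one listed factor at a time. C.2.3 enters many together, so these figures show the mechanism and do not predict the planned model's error rate.

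**The case against.** **The lists are open.** Each begins with a word meaning including, and the models are described by category, so severity could be added without contradicting the text. That is fair: the gap is incomplete pre-specification, not stated exclusion. But the models are tied to the factors listed above them, and no other covariate is named.

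**C.2.1 already adjusts for baseline health.** Its sensitivity analysis for the primary outcome includes unnamed demographic and health covariates, and the H3 text in C.2.2 spells out a similar phrase as FEV1 percent predicted, comorbidities, depressive symptoms and exacerbations. On that reading the Charlson index has an implied place in C.2, and part of C.4.1's worry about imbalance is met. Adjusting the treatment comparison does not, however, show whether severity rather than a muscle or mood factor explains response, which is what C.4.3 asks.

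**A.3.4.1 concerns exercise tolerance, not change in 6MWT.** This stands. The documents do not show that FEV1 predicts the gain, so the FEV1 figures are illustrative only. The baseline 6MWT figure does not depend on that passage.

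**The stakes are low.** The objective is exploratory, the C.2.3 heading carries a note that it is not reported, and C.4.3 would only explore further interventions after a failed trial. This limits the severity.

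**Conclusion.** The mismatch is real but minor. Severity of lung disease and baseline fitness are sent to an analysis whose listed factors include neither, and model (a) has no baseline 6MWT term. The best-founded size is 7% to 27% false positives in model (a), resting on ρ = 0.70, equal SDs, n = 136 and an assumed correlation of 0.1 to 0.3 between the factor and baseline 6MWT.

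A reader might infer more than the documents support:
- That none of the C.4 factors is listed. C.2.3 does list number and severity of exacerbations, most naturally those monitored during the study under C.1.10. Only pre-study history is unnamed.
- That C.1.9.5.c sends comorbidity to the exploratory analysis. It cites C.2 as a whole; the supportable point is that no C.2 model names the index.
- That the muscle and mood factors will absorb the omitted effects. They may, if correlated with them. With zero correlation the rate stays at 5%, and the documents give no such correlations.
- That the treatment comparison is biased. Randomization protects it from these omissions.

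**What to change.** - Add baseline FEV1 percent predicted to both C.2.3 models.
- Add baseline 6MWT to model (a) only, using the same baseline value that forms the change score. Model (b) already has it as an outcome, so it should not also be a predictor there.
- Add the Charlson index to both models, or state which C.2 model uses it, so that C.1.9.5.c has a named analysis.
- Add pre-study exacerbation history only if the screening history records it. C.1.5 mentions medical history in general and Table 4 has no exacerbation item. Otherwise remove that pointer from C.4.1.
- If the exploratory objective will not be analysed, correct the pointers in C.4.1 and C.4.3 instead.

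Pulmonary function, the Charlson index and the standard 6MWT are already scheduled at screening or baseline in Table 4, so for these the change is SAP wording. The cost is two to four degrees of freedom in an exploratory model with about 136 patients.
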